3.2 Exclusion Criteria

- 3.2.1 Participants who have had chemotherapy, targeted small molecule therapy or study therapy within 5 days of protocol treatment, or those who have not recovered (i.e., \leq Grade 1 or at baseline) from adverse events due to agents administered more than 2 weeks earlier. Subjects with \leq Grade 2 neuropathy are an exception to this criterion and may qualify for the study. If subject received major surgery, they must have recovered adequately from the toxicity and/or complications from the intervention prior to starting therapy.
- 3.2.2 Participants who are receiving any other investigational agents.
- 3.2.3 Patients should be excluded if they have an active, known or suspected autoimmune disease. Subjects are permitted to enroll if they have vitiligo, type I diabetes mellitus, residual hypothyroidism due to autoimmune condition only requiring hormone replacement, psoriasis not requiring systemic treatment, or conditions not expected to recur in the absence of an external trigger
- 3.2.4 Patients should be excluded if they have a condition requiring systemic treatment with either corticosteroids (> 10 mg daily prednisone equivalents) or other immunosuppressive medications within 14 days of study drug administration. Inhaled or topical steroids and adrenal replacement doses > 10 mg daily prednisone equivalents are permitted in the absence of active autoimmune disease. Subjects are permitted to use topical, ocular, intra-articular, intranasal, and inhalational corticosteroids (with minimal systemic absorption). Physiologic replacement doses of systemic corticosteroids are permitted, even if > 10 mg/day prednisone equivalents. A brief course of corticosteroids for prophylaxis (eg, contrast dye allergy) or for treatment of non-autoimmune conditions (eg, delayed-type hypersensitivity reaction caused by contact allergen) is permitted.
- 3.2.5 As there is potential for hepatic toxicity with nivolumab or nivolumab/ipilimumab combinations, drugs with a predisposition to hepatotoxicity should be used with caution in patients treated with nivolumab-containing regimen.

- 3.2.6 Patients should be excluded if they have had prior systemic treatment with a combination of anti-CTLA4 antibody and anti-PD1/PDL1 antibody. Prior treatment with single agent anti-CTLA4, anti-PD1 or anti-PDL1 antibody is allowed.
- 3.2.7 Has a known history of active TB (Bacillus Tuberculosis)
- 3.2.8 Patients should be excluded if they are positive test for hepatitis B virus surface antigen (HBV sAg) or hepatitis C virus ribonucleic acid (HCV antibody) indicating acute or chronic infection
- 3.2.9 Patients should be excluded if they have known history of testing positive for human immunodeficiency virus (HIV) or known acquired immunodeficiency syndrome (AIDS). These participants are at increased risk of lethal infections when treated with marrow-suppressive therapy. Appropriate studies will be undertaken in participants receiving combination antiretroviral therapy when indicated.
- 3.2.10 Uncontrolled intercurrent illness including, but not limited to, ongoing or active infection, symptomatic congestive heart failure, unstable angina pectoris, cardiac arrhythmia, or psychiatric illness/social situations that would limit compliance with study requirements.
- 3.2.11 Has known psychiatric or substance abuse disorders that would interfere with cooperation with the requirements of the trial.
- 3.2.12 Is pregnant or breastfeeding, or expecting to conceive or father children within the projected duration of the trial, starting with the pre-screening or screening visit through 120 days after the last dose of trial treatment.
- 3.2.13 Has a known additional malignancy that is progressing or requires active treatment. Exceptions include basal cell carcinoma of the skin or squamous cell carcinoma of the skin that has undergone potentially curative therapy or in situ cervical cancer.
- 3.2.14 Has known history of, or any evidence of active, non-infectious pneumonitis.
- 3.2.15 Has an active infection requiring systemic therapy.
- 3.2.16 Has received a live vaccine within 30 days of planned start of study therapy. Note: Seasonal influenza vaccines for injection are generally inactivated flu vaccines and are allowed; however intranasal influenza vaccines (e.g., Flu-Mist®) are live attenuated vaccines, and are not allowed.
- 3.2.17 History of allergy to study drug components
- 3.2.18 History of severe hypersensitivity reaction to any monoclonal antibody

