3. PARTICIPANT SELECTION

3.1 Eligibility Criteria

- 3.1.1 Participants must have histologically or cytologically confirmed disease from any solid tumor.
- 3.1.2 Age ≥ 18 years.
- 3.1.3 ECOG performance status ≤ 2 (Karnofsky $\geq 60\%$, see Appendix A)
- 3.1.4 Life expectancy of greater than 3 weeks
- 3.1.5 Participants must have normal organ and marrow function as defined in Table 1, all screening labs should be performed within 14 days of treatment initiation.

Table 1 Adequate Organ Function Laboratory Values

System	Laboratory Value
Hematological	
Absolute neutrophil count (ANC)	≥ 1500 /mcL

Platelets	$\geq 100,000 / \text{mcL}$
Hemoglobin	$\geq 9 \text{ g/dL}$ or $\geq 5.6 \text{ mmol/L}$ without transfusion or EPO dependency (within 7 days of assessment)
Renal	
Serum creatinine OR Measured or calculated ^a creatinine clearance (GFR can also be used in place of creatinine or CrCl)	
$\leq \text{ Serum creatinine} \leq 1.5 \times \text{ULN}$ or creatinine clearance (CrCl) $\geq 40 \text{ mL/min}$ (if using the Cockcroft-Gault formula below):
 
Female CrCl = $(140 - \text{age in years}) \times \text{weight in kg} \times 0.85$ $72 \times \text{serum creatinine in mg/dL}$
 
Male CrCl = $(140 - \text{age in years}) \times \text{weight in kg} \times 1.00$ $72 \times \text{serum creatinine in mg/dL}$

Hepatic	
Serum total bilirubin	$\leq 1.5 \times \text{ULN}$ OR
	Direct bilirubin $\leq \text{ULN}$ for subjects with total bilirubin levels $> 1.5 \text{ ULN}$
AST (SGOT) and ALT (SGPT)	$\leq 3 \text{ ULN}$ OR $\leq 5 \times \text{ULN}$ for subjects with liver metastases
Albumin	$\geq 2.5 \text{ mg/dL}$
Coagulation	
International Normalized Ratio (INR) or Prothrombin Time (PT)	$\leq 1.5 \times \text{ULN}$ unless subject is receiving anticoagulant therapy as long as PT or PTT is within therapeutic range of intended use of anticoagulants
Activated Partial Thromboplastin Time (aPTT)	$\leq 1.5 \times \text{ULN}$ unless subject is receiving anticoagulant therapy as long as PT or PTT is within therapeutic range of intended use of anticoagulants

^aCreatinine clearance should be calculated per institutional standard.

- 3.1.6 Women of childbearing potential (WOCBP) must use appropriate method(s) of contraception. WOCBP should use an adequate method to avoid pregnancy for 23 weeks (30 days plus the time required for nivolumab to undergo five half-lives) after the last dose of investigational drug.

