5.2 Pre-Treatment Criteria

5.2.1 Cycle 1, Day 1

A serum or urine pregnancy testing is required within 72 hrs of study enrollment. Cycle 1, Day 1 labs will be used to confirm eligibility.

System	Laboratory Value
Hematological	
Absolute neutrophil count (ANC)	$\geq 1500 / \text{mcL}$
Platelets	$\geq 100,000 / \text{mcL}$
Hemoglobin	$\geq 9 \text{ g/dL}$ or $\geq 5.6 \text{ mmol/L}$ without transfusion or EPO dependency (within 7 days of assessment)
Renal	
Serum creatinine OR Measured or calculated ^a creatinine clearance (GFR can also be used in place of creatinine or CrCl)	$\leq \text{ Serum creatinine} \leq 1.5 \times \text{ULN}$ or creatinine clearance (CrCl) $\geq 40 \text{ mL/min}$ (if using the Cockcroft-Gault formula below): $\text{Female CrCl} = \frac{(140 - \text{age in years}) \times \text{weight in kg} \times 0.85}{72 \times \text{serum creatinine in mg/dL}}$ $\text{Male CrCl} = \frac{(140 - \text{age in years}) \times \text{weight in kg} \times 1.00}{72 \times \text{serum creatinine in mg/dL}}$
Hepatic	
Serum total bilirubin	$\leq 1.5 \times \text{ULN}$ OR
	Direct bilirubin $\leq \text{ULN}$ for subjects with total bilirubin levels $> 1.5 \text{ ULN}$
AST (SGOT) and ALT (SGPT)	$\leq 3 \text{ ULN}$ OR $\leq 5 \times \text{ULN}$ for subjects with liver metastases
Albumin	$\geq 2.5 \text{ mg/dL}$
Coagulation	
International Normalized Ratio	$\leq 1.5 \times \text{ULN}$ unless subject is receiving anticoagulant therapy

(INR) or Prothrombin Time (PT)	as long as PT or PTT is within therapeutic range of intended use of anticoagulants $\leq 1.5 \times \text{ULN}$ unless subject is receiving anticoagulant therapy
Activated Partial Thromboplastin Time (aPTT)	as long as PT or PTT is within therapeutic range of intended use of anticoagulants
^a Creatinine clearance should be calculated per institutional standard.	

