7.5 Definitions

7.5.1 An **Adverse Event (AE)** is defined as any new untoward medical occurrence or worsening of a preexisting medical condition in a clinical investigation subject administered an investigational (medicinal) product and that does not necessarily have a causal relationship with this treatment. An AE can therefore be any unfavorable and unintended sign (such as an abnormal laboratory finding), symptom, or disease temporally associated with the use of investigational product, whether or not considered related to the investigational product. The causal relationship to study drug is determined by a physician and should be used to assess all adverse events (AE).

7.5.2 A **Serious Adverse Event (SAE)** is any untoward medical occurrence that at any dose:

- results in death
- is life-threatening (defined as an event in which the subject was at risk of death at the time of the event; it does not refer to an event which hypothetically might have caused death if it were more severe)
- requires inpatient hospitalization or causes prolongation of existing hospitalization (see **NOTE** below)
- results in persistent or significant disability/incapacity
- is a congenital anomaly/birth defect
- is an important medical event (defined as a medical event(s) that may not be immediately life-threatening or result in death or hospitalization but, based upon appropriate medical and scientific judgment, may jeopardize the subject or may require intervention [eg, medical, surgical] to prevent one of the other serious outcomes listed in the definition above.) Examples of such events include, but are not limited to, intensive treatment in an emergency room or at home for allergic bronchospasm; blood dyscrasias or convulsions that do not result in hospitalization.)
- Potential drug induced liver injury (DILI) is also considered an important medical event.
- Suspected transmission of an infectious agent (eg, pathogenic or nonpathogenic) via the study drug is an SAE.
- Although pregnancy, overdose, and cancer are not always serious by regulatory definition, these events must be handled as SAEs.

The following hospitalizations are not considered SAEs:

- a visit to the emergency room or other hospital department < 24 hours, that does not result in admission (unless considered an important medical or life-threatening event)
- elective surgery, planned prior to signing consent
- admissions as per protocol for a planned medical/surgical procedure

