10. STUDY CALENDAR

Baseline evaluations are to be conducted within 14 days prior to start of protocol therapy, with the exception of CSF with positive cytology, which must be done \leq 6 weeks prior to initiation of study treatment. Also, if patients received other chemotherapy or targeted therapy within 14 days prior to start of protocol therapy, CBC and serum chemistry (including LFTs and creatinine) should be done within 5 days prior to start of protocol therapy. Scans and x-rays must be done \leq 4 weeks prior to the start of therapy. In the event that the participant's condition is deteriorating, laboratory evaluations should be repeated within 48 hours prior to initiation of the next cycle of therapy.

Assessments must be performed prior to administration of any study agent. Study assessments and agents should be administered within \pm 3 days of the protocol-specified date, unless otherwise noted.

Calendar During Induction Phase for Melanoma, Small Cell Lung Cancer, Breast Cancer, Bladder Cancer, Renal Cancer and Other Solid Tumors

	Pre-Study	Wk 1	Wk 2	Wk 3	Wk 4	Wk 5	Wk 6	Wk 7	Wk 8	Wk 9	Wk 10	Wk 11	Wk 12	Off Study ^h	Follow-up visits ⁱ
Ipilimumab		A			A			A			A				
Nivolumab		B			B			B			B				
Informed consent ^a	X														
Demographics ^a	X														
Medical history ^a	X														
Concurrent meds	X	X-----X													
Physical exam ^b	X	X	X	X	X	X	X	X	X	X	X	X	X	X	X
Vital signs	X	X	X	X	X	X	X	X	X	X	X	X	X	X	X
Height	X														
Weight	X	X			X			X			X			X	X
Performance status	X	X			X			X			X			X	X
CBC w/diff, plts	X	X			X			X			X			X	X
Serum chemistry ^c	X	X			X			X			X			X	X
EKG (as indicated) ^d	X														
Adverse event evaluation		X-----X												X	X
Tumor measurements	X	Tumor measurements are repeated every 6 weeks. Documentation (radiologic) must be provided for participants removed from study for progressive disease.												X	
Radiologic evaluation	X	Radiologic measurements should be performed every 6 weeks (Brain MRI and CT Chest/Abd/Pelvis)												X	X
B-HCG	X ^e							X							X
Cerebrospinal fluid	X ^f	X			X			X			X				
Blood ⁱ	X	X			X			X			X			X	X
Archival tissue ^g	X													X	X

A: For melanoma, small cell lung cancer, breast cancer, bladder cancer and other solid tumors (except NSCLC and head and neck cancers): Ipilimumab 3mg/kg every 3 weeks x 4 doses during induction.. For renal cell cancer: Ipilimumab 1mg/kg every 3 weeks x 4 doses during induction.

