13.6 Analysis of Secondary Endpoints

Safety and Tolerability: All adverse events recorded during the trial will be summarized for all patients having received one or more doses of ipilimumab and nivolumab. The data for each cohort will be summarized separately, although safety data may be combined, if appropriate. The proportions of patients with grade-3 or higher hematologic toxicities or grade-3 or higher neurologic toxicities will be presented with 90% exact binomial confidence intervals. The incidence of events that are new or worsening from the time of first dose of treatment will be summarized according to system organ class and/or preferred term, severity (based on CTCAE grade), type of adverse event, and relation to study treatment. Deaths reportable as SAEs and non-fatal serious adverse events will be listed by patient and tabulated by primary system organ class, and type of adverse event.

Intracranial/Extracranial Response: The proportion of patients with intracranial response of intraparenchymal brain metastases (CR or PR by RANO) will be presented with a two-sided, 90% exact binomial confidence interval. For a sample of 18 patients, the confidence interval will have maximum width of 0.42. Extracranial response rates (CR or PR) according to RECIST and irRC will be summarized. Rates will be accompanied by two-sided 90% exact binomial

confidence intervals. Cases where RECIST and irRC responses do not agree will be documented.

Leptomeningeal Disease Response: The proportion of patients with leptomeningeal disease response (CR or PR) will be presented with a two-sided, 90% exact binomial confidence interval. For a sample of 18 patients, the confidence interval will have maximum width of 0.42.

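### Exclusion 3.2.1 requires no toxicity recovery for drugs last given 6 to 14 days before treatment, and 13.6 sets no baseline or attribution rule for the Grade 3+ toxicity proportions

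*Combined protocol and SAP*

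**What the plan says.** Exclusion 3.2.1 contains two time limits.

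- Washout: a patient is excluded after "chemotherapy, targeted small molecule therapy or study therapy within 5 days of protocol treatment".
- Recovery: a patient is excluded if not back to Grade 1 or baseline from "adverse events due to agents administered more than 2 weeks earlier". Subjects with neuropathy up to "Grade 2 neuropathy are an exception to this criterion and may qualify for the study".

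Other sections bear on the same patients.

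- Section 3.1.5: "Participants must have normal organ and marrow function as defined in Table 1". These limits do not depend on the date of the last drug. Section 5.2.1 repeats the table and adds that "Cycle 1, Day 1 labs will be used to confirm eligibility".
- Section 10: "if patients received other chemotherapy or targeted therapy within 14 days prior to start of protocol therapy, CBC and serum chemistry" are to be done within 5 days before the start.
- Exclusions 3.2.10, 3.2.14 and 3.2.15 cover uncontrolled intercurrent illness, non-infectious pneumonitis, and infection needing systemic therapy.
- Section 7.5.1 defines an adverse event as "any new untoward medical occurrence or worsening of a preexisting medical condition".
- Section 13.1 names Grade 3 or higher hematologic and neurologic toxicity as a secondary endpoint. Section 13.6 reports these proportions with 90% exact intervals. A separate sentence there covers general incidence: "The incidence of events that are new or worsening from the time of first dose of treatment will be summarized", with relation to treatment as one of the breakdowns.

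**The concern.** The two limits in 3.2.1 do not meet. A site that follows the text literally can enroll a patient who still has clinical toxicity from a drug given the week before, provided that no other criterion catches it. The neuropathy exception suggests that the authors meant higher grades to exclude. Yet Grade 3 neuropathy from a drug given ten days earlier is not excluded by 3.2.1. Section 6 is stricter once treatment has begun: dosing is delayed for most non-skin drug-related events of Grade 2 or higher, and in general resumes only at Grade 1 or baseline.

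Two things are at stake. One is the safety of patients who start two checkpoint antibodies with active toxicity from an earlier drug. The other is the meaning of the Grade 3+ proportions, which readers will take as the toxicity of nivolumab plus ipilimumab.

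**Working it through.** The plan states no figure on this point, so there is none to reproduce. The check compares the windows and then sizes the effect of one patient.

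**1. The windows in 3.2.1.** I count in whole days, taking day 5 as inside the washout and day 14 as not yet more than 2 weeks.

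| Last dose before treatment | Washout clause | Recovery clause |
|---|---|---|
| 0 to 5 days | excludes | not needed |
| 6 to 14 days | allows | does not apply |
| 15 days or more | allows | applies |

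Uncovered days: 14 − 6 + 1 = 9.

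**2. Whether such patients are foreseen.** Section 10 sets a special laboratory timing for chemotherapy or targeted therapy in the 14 days before the start. After the 5-day washout, the patients to whom that rule can apply are those in the 6 to 14 day row.

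**3. What other criteria catch.** Table 1 covers blood counts, renal and hepatic function, albumin and coagulation. Values beyond its limits when sampled exclude the patient whatever the last-dose date. Exclusions 3.2.10, 3.2.14 and 3.2.15 catch selected clinical conditions. What remains is other non-laboratory toxicity, such as diarrhea, rash or neuropathy.

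**4. What can be counted afterwards.**

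- Toxicity present at entry that does not worsen is not an adverse event under 7.5.1, and it falls outside the general incidence summary.
- Toxicity that worsens or first appears after the first dose is an adverse event, whichever drug caused it.
- The sentence in 13.6 on the Grade 3+ proportions says nothing about attribution or baseline grade. Section 13.8.1 makes patients evaluable for toxicity from first treatment. A Grade 3 event caused by the prior drug can therefore be counted.

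**5. Size per patient.** Section 13.2 gives 18 evaluable patients and accrual of up to 20. The safety set is defined by dosing, so its denominator may exceed 18.

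- Shift per patient = 1/n: 1/18 = 5.6 points; 1/20 = 5.0 points.
- Example at n = 18, with 90% exact (Clopper-Pearson) intervals: 2/18 = 11.1% (2.0% to 31.0%) against 3/18 = 16.7% (4.7% to 37.7%).

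**The case against.** The case on the other side is substantial, and much of it stands.

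- **Laboratory toxicity is screened.** A reader might infer from 3.2.1 that any unresolved Grade 2 to 4 event from the 6 to 14 day window is admissible. The documents do not support that. Table 1 applies to everyone, 5.2.1 repeats it, and Section 10 adds a check for exactly these patients.
- **Stable carry-over is not counted.** A reader might also infer that toxicity already present at entry is scored against the study drugs. Section 7.5.1 rules that out unless the event worsens.
- **Attribution is collected.** Section 7.1 grades it on five levels, and the general summary in 13.6 uses relation to treatment. The gap is that the Grade 3+ proportions do not say whether they use it.
- **A large distortion cannot be shown.** If 2 to 5 of 18 patients entered in the window, 2/18 = 11 to 5/18 = 28 points might seem at risk. That assumes the share of patients. It also assumes that every one of them has a Grade 3+ event caused by the prior drug and would not otherwise be counted. The documents support neither assumption.
- **Closing the gap would not prevent every carry-over.** A patient given chemotherapy 6 days before treatment and sampled 5 days before could pass Table 1, and the counts could fall after day 1. That risk comes from the length of the washout. Only the analysis can make it visible.
- **A short washout is understandable.** Section 2.1 puts untreated median survival at about 4 to 6 weeks. That explains early entry, but not why recovery is required for older drugs and not for recent ones.
- **The consequence is limited.** Toxicity is a descriptive secondary endpoint with no threshold attached. Survival at 3 months and the two-stage rule do not depend on it.

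**Conclusion.** The point holds in a limited form. Read literally, 3.2.1 requires no recovery from agents last given 6 to 14 days before treatment, and the other criteria do not close the gap for most non-laboratory toxicity. Separately, the Grade 3+ hematologic and neurologic proportions in 13.6 have no stated baseline or attribution rule, so a worsening or delayed effect of a prior drug can be counted in them.

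The size that can be defended is 5.6 points per affected patient at n = 18, or 5.0 at n = 20. No total can be given, because the number of patients in the window is not stated. The 9-day figure rests on the whole-day counting shown above. The primary endpoint and the sample size are unaffected.

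**What to change.** 1. **Section 3.2.1.** The sponsor should reconcile the washout and recovery clauses with each other and with the 14-day rule in Section 10, so that no permitted prior agent falls outside both clauses. The choice of period is the sponsor's.
2. **Section 13.6.** Present the Grade 3+ hematologic and neurologic events with each patient's baseline grade and the recorded attribution, and say how these enter the proportions.
3. **Section 13.6.** List or tabulate separately the patients with chemotherapy or targeted therapy in the 14 days before first dose. Sites need that date already to apply the Section 10 rule. A listing is enough if there are few: with 2 patients, 1/2 has a 90% exact interval of about 2.5% to 97.5%.

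The cost is a change to one eligibility criterion, a short addition to the analysis text, and one small descriptive table or listing. Screening already includes blood counts and a neurologic examination, although a baseline neurologic grade may have to be recorded explicitly. The downside is that an occasional patient may enter later.
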